**Table 10-1: CTCAE v4.03 General Guidelines**

Grade	Description
Grade 1	Mild; asymptomatic or mild symptoms; clinical or diagnostic observations only; intervention not indicated.
Grade 2	Moderate; minimal, local, or noninvasive intervention indicated; limiting age-appropriate instrumental activities of daily living (ADL)*.
Grade 3	Severe or medically significant but not immediately life-threatening; hospitalization or prolongation of hospitalization indicated; disabling; limiting self care ADL†.
Grade 4	Life-threatening consequences; urgent intervention indicated.
Grade 5	Death related to AE.

\*Instrumental ADL refer to preparing meals, shopping for groceries or clothes, using the telephone, managing money, etc.

†Self care ADL refer to bathing, dressing and undressing, feeding self, using the toilet, taking medications, and not bedridden.

-Common Terminology Criteria for Adverse Events (CTCAE), v4.03: June 14, 2010

### 10.2.3 CAUSALITY ASSESSMENT

Adverse events will be assigned a relationship (causality) to the study treatment. The Principal Investigator must review each AE and make the determination of relationship of the event to the study treatment. Relationship of AEs to study treatment will be classified as follows:

1. **Definitely related:** This category applies to those AEs that the Investigator feels are incontrovertibly related to the study treatment. An AE may be assigned an attribution of definitely related if or when it meets all of the following criteria: (1) it follows a reasonable temporal sequence from administration of the study treatment; (2) it could not be reasonably explained by the known characteristics of the subject's clinical state, environmental or toxic factors, or other modes of therapy administered to the subject; (3) it follows a known response pattern to treatment with the study treatment.
2. **Probably related:** This category applies to those AEs which, after careful medical consideration at the time they are evaluated, are felt with a high degree of certainty to be related to the study treatment. An AE may be considered probable if or when (must have three): (1) it follows a reasonable temporal sequence from administration of the study treatment. (2) It could not readily have been produced by subject's clinical state, environmental or toxic factors, or other therapies administered to the subject. (3) Disappears or is decreased upon discontinuation of the study treatment. (4) It follows a known response pattern to treatment with the study treatment.
3. **Possibly related:** This category applies to those AEs which, after careful medical consideration at the time they are evaluated, are judged unlikely but cannot be ruled out with certainty to the study treatment. An AE may be considered possible if or when (must have two): (1) it follows a reasonable temporal sequence from administration of the study treatment. (2) It could not readily have been produced by subject's clinical state, environmental or toxic factors, or other therapies administered to the subject. (3) Disappears or is decreased upon discontinuation of the study treatment. (4) It follows a known response pattern to treatment with the study treatment.
4. **Remotely related:** In general this category can be considered applicable to those AEs which, after careful medical consideration at the time they are evaluated, are judged likely to be unrelated to the study treatment. An AE may be considered unlikely if or when (must have two): (1) it does not follow a reasonable temporal sequence from administration of the study treatment. (2) It could not readily have been produced by subject's clinical state, environmental or toxic factors, or other therapies administered to the subject. (3) Disappears or is decreased upon discontinuation of the study treatment. (4) It does not follow a known response pattern to treatment with the study treatment.
5. **Unrelated:** This category applies to those AEs which, after careful consideration at the time they are evaluated, are clearly and incontrovertibly due to extraneous causes (disease, environment, etc.) and determined with certainty to have no relationship to the study treatment.

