### 10.2.1 IMPACT ON STUDY TREATMENT

The impact the event had on the study treatment will be assessed as either: none, study treatment interrupted, study treatment discontinued, or not applicable. The "not applicable" assessment will be used only when the subject is no longer in the treatment phase of the protocol, or if the outcome of the event was "death".

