8.3.1 Adverse Events

Adverse events will be coded using the most recent version of Medical Dictionary for Regulatory Activities (MedDRA). Treatment Emergent AE's (TEAE) are defined as events with an onset on or after the first randomized treatment. TEAEs will be summarized by treatment group, System Organ Class, and preferred term. The following TEAE summaries will be provided:

- Overall (*i.e.*, regardless of severity or relationship to treatment)
- By severity grade (mild, moderate, severe, life threatening or death for SAEs)
- By relationship to clinical trial treatment according to the mapping scheme below:
 - Potentially related: will include all adverse events with a relationship rating of “definitely”, “probably” or “possibly”.
 - Unlikely/not related: will include all adverse events with a relationship rating of “unlikely” or “unrelated”.

Unless otherwise specified, at each level of subject summarization, a subject will be counted only once. If there is more than one occurrence of an event, the event of the worst severity or the worst-case relationship category will be summarized.

In addition, separate summaries of serious adverse events, and adverse events resulting in discontinuation of study treatment will be presented.

AEs leading to premature discontinuation of clinical trial treatment, AEs that lead to study discontinuation, AEs that lead to death and Serious Adverse Events (SAEs) will also be summarized by treatment group and relationship.

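### Remotely related (Protocol 10.2.3) repeats two criteria of Possibly related un-negated, so one AE can fall on either side of the SAP's related/not-related split

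*Protocol*

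**What the plan says.** Protocol 10.2.3 leaves the grade to the investigator: "The Principal Investigator must review each AE and make the determination of relationship of the event to the study treatment". It offers five categories, and for all but Unrelated it lists criteria to guide the choice.

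- **Possibly related (item 3)** covers AEs that "are judged unlikely but cannot be ruled out with certainty to the study treatment". Its rule is "An AE may be considered possible if or when (must have two"), followed by four criteria: (1) reasonable timing, (2) no other ready cause, (3) improvement on stopping, (4) a known response pattern. Probably related uses the same four but asks for three.
- **Remotely related (item 4)** covers AEs that "are judged likely to be unrelated to the study treatment". Its rule is "An AE may be considered unlikely if or when (must have two"). Criterion (1) becomes timing that is *not* reasonable. Criterion (2) is the same sentence as in item 3. The last two read "3) Disappears or is decreased upon discontinuation of the study treatment. (4) It does not follow a known response pattern to treatment": (3) is again unchanged, and (4) is negated.

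SAP 8.3.1 then splits the grades in two. One group is defined by "Potentially related: will include all adverse events with a relationship rating of" definitely, probably or possibly; the other takes *unlikely* and *unrelated*. The SAP has no category called remotely. The link is item 4's own use of the word unlikely.

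**The concern.** Having no other ready explanation, and resolving when the drug is stopped, are evidence for a drug effect. Items 2 and 3 use them that way. Item 4 uses the same two facts as evidence that the AE is likely unrelated. Because items 3 and 4 both ask for two criteria, an AE showing just those two facts meets both.

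The lead definitions do not settle the matter. Possibly is for AEs already judged unlikely but not ruled out, and Remotely is for AEs judged likely to be unrelated. An investigator who looks to the criteria to separate these finds that they overlap at exactly this boundary, which is where SAP 8.3.1 divides related from not related.

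What is at stake is the by-relationship tables for TEAEs, SAEs, AEs leading to death and AEs leading to discontinuation, in a trial whose primary objective is safety and tolerability. Two investigators could place the same kind of AE on opposite sides.

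**Working it through.** The documents give no figure to reproduce; the check is on the logic of the definitions.

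**Inputs (Protocol 10.2.3).** Four yes/no facts, scored 1 or 0: T = reasonable timing, N = no other ready cause, D = improves on stopping, K = known response pattern. The slightly different wording of the no-other-cause criterion under Definitely is treated as the same fact. *Must have two* is read as at least two.

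**Rules.**
- Definitely: T, N and K all 1
- Probably: T + N + D + K ≥ 3
- Possibly: T + N + D + K ≥ 2
- Remotely as written: (1−T) + N + D + (1−K) ≥ 2

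**All 16 patterns, as written.**
- Both Possibly and Remotely: TN, TD, ND, NK, DK, TND, NDK, TNDK = 8
- Possibly only: TK, TNK, TDK = 3
- Remotely only: none of the four, N, D = 3
- Neither: T, K = 2

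Check: 8 + 3 + 3 + 2 = 16. Possibly is met by 8 + 3 = 11 patterns and Remotely by 8 + 3 = 11. Within the 8 lie 3 of the 5 Probably patterns (TND, NDK, TNDK) and 1 of the 2 Definitely patterns (TNDK), all with D = 1. If *must have two* means exactly two, each category has 6 patterns and 4 are shared, so the overlap does not depend on that reading.

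**Split by whether treatment was stopped.** Protocol 10.2.1 allows for AEs with no effect on treatment: "The impact the event had on the study treatment will be assessed as either: none, study treatment interrupted, study treatment discontinued, or not applicable". For these D cannot be met.

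| Situation | Meet Possibly | Also meet Remotely |
|---|---|---|
| Not stopped (D cannot be met) | 4 | 2 (TN, NK) |
| Stopped and improved (D = 1) | 7 | 6 |

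Worked example, treatment continuing, with T = 1, N = 1, D = 0, K = 0:
- Possibly: 1 + 1 + 0 + 0 = 2, met.
- Remotely: 0 + 1 + 0 + 1 = 2, met.

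**No known pattern.** The drug is first-in-human (Protocol 1.4) and no AEs are expected (Protocol 10.3). Assuming that investigators therefore find no known response pattern (K = 0), all 4 patterns that meet Possibly (TN, TD, ND, TND) also meet Remotely. This is an assumption, since the component botanicals have prior human use.

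**After reversing (2) and (3) in item 4.**
- Treatment stopped: Remotely becomes (1−T) + (1−N) + (1−D) + (1−K) ≥ 2, that is T + N + D + K ≤ 2. The overlap with Possibly is the 6 patterns with exactly two facts. The overlaps with Probably and Definitely fall to 0, and no pattern meets neither category.
- Not stopped, (3) not applied: Remotely becomes T + N + K ≤ 1, against T + N + K ≥ 2 for Possibly. Overlap 0 of 4; no pattern meets neither.
- Not stopped, reversed (3) counted as met: Remotely becomes T + N + K ≤ 2. Overlap 3 of 4, worse than the 2 of 4 as written.

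**The case against.** The strongest reply is that these are guides to a judgement, not an algorithm. The wording is permissive, one grade per AE is required, and the scale already overlaps by design: all 5 Probably patterns also meet Possibly. An investigator who works down from the top would grade all 8 overlapping patterns Possibly or higher. That is a sensible reading, but it is not written anywhere. For clashes with Probably and Definitely, the lead definitions largely do the job; for Possibly against Remotely they do not.

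Four further points stand in part.

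- **Cause.** The copied criteria are not the only source of overlap. With two-of-four thresholds on both sides, 6 ties survive reversal where treatment was stopped, so reversal alone is not a complete fix.
- **Counts.** They weight logical patterns equally and say nothing about how often each occurs.
- **SAP label.** The SAP does not name Remotely, so its place on the not-related side is inferred from item 4's own wording. No other protocol category corresponds to *unlikely*.
- **Consequences.** All SAEs are reported whatever their relationship (Protocol 10.5), and SAP 8.3.1 takes the worst-case relationship for repeated events. Conversely, the listings will show the recorded grade, but Protocol 10.2 does not ask for the criteria behind it, so inspecting borderline AEs has limits. Criterion (3) also operates only after stopping, so if stopping differs by arm the ambiguity may not arise equally often.

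**Conclusion.** The concern holds. Item 4 counts two pointers towards a drug effect as pointers away from one, and this lets the same AE fit two categories on opposite sides of the SAP 8.3.1 split. Read literally, the overlap is 8 of the 11 patterns that meet Possibly: 2 of 4 where treatment is not stopped, 6 of 7 where it is stopped and the AE improves.

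Severity is minor. Investigators are blinded (Protocol 9.5) and the wording does not refer to any arm. Overall TEAE incidence does not change, and none of the safety outcomes in Protocol 9.2.1 or SAP 3.2 is defined by relationship. The damage is confined to descriptive by-relationship tables. The conclusion assumes that investigators use the listed criteria to separate adjacent categories. The documents do not allow an estimate of how many AEs would be graded differently.

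**What to change.** 1. **Reverse (2) and (3) in item 4 (main change).** Criterion (2) should be met when the AE could readily be explained by something other than study treatment. Criterion (3) should be met when the AE does not improve after stopping, and should apply only where study treatment was stopped. That limit is needed: with it the not-stopped overlap goes from 2 of 4 to 0 of 4, without it to 3 of 4.
2. **Add a tie rule.** If, after applying the lead definitions, the investigator still finds that both Possibly and Remotely fit, the more related category is recorded. This deals with the 6 remaining ties where treatment was stopped. It also means that whether an interruption or the planned end of treatment counts as stopped for item 4 does not alter the choice between the two in a tie.
3. **Align the label.** In the SAP 8.3.1 mapping, replace *unlikely* with the protocol's Remotely related.

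The cost is a short amendment to the protocol and CRF guidance and one SAP line. AEs already graded Remotely need a blinded re-review. The related-AE count may rise in any arm, by an amount the documents do not allow to be estimated.

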### 10.2.4 TREATMENT GIVEN AS A RESULT OF THE EVENT

The event impact in terms of treatment provided will be as either: none, medication administered, non-medication therapy administered, surgery, or other (with a specification).

### 10.2.5 OUTCOME ASSESSMENT

The outcome of the event will be assessed as either: resolved, resolved with sequelae, ongoing, or death. Only one AE per subject is allowed to have an outcome assessment as "death." If there are

multiple causes of death for a given subject, only the primary cause of death will have an outcome of death.

### **10.3 EXPECTED / ANTICIPATED ADVERSE EVENTS**

There are no expected AEs associated with participation in this study.

### **10.4 SERIOUS ADVERSE EVENTS**

A SAE is defined as any AE that:

- Results in death
- Is life threatening (the subject is at immediate risk of dying from the AE)
- Requires subject hospitalization or prolongs existing hospitalization
- Results in persistent or significant disability/incapacity
- Is a congenital anomaly/birth defect
- Important medical events that may not result in death, be life-threatening, or require hospitalization may be considered serious when, based upon appropriate medical judgment, they may jeopardize the subject and may require medical or surgical intervention to prevent one of the outcomes listed in this definition.

### **10.5 REPORTING OF SERIOUS ADVERSE EVENTS (SAE)**

The Investigator is required to report all SAEs that occur during the time period specified in [Section 10.2](#). Once the Investigator becomes aware of an SAE, he/she must report the SAE to Amarex Safety Department within 24 hours:

CRO Medical Monitor	Attn: [name] Amarex LLC [name] [name] Email: [contact] [contact] [contact]
----------------------------	--

A written report, including a full description of the event as described in [Section 10.2](#), must follow within 24 hours from the time the Investigator first learned of the event. The Amarex Medical Monitor may request additional supporting documentation as it becomes available, such as lab reports, ECG reports, discharge summary, hospital notes, etc.

The Investigator is also responsible for reporting all SAEs to the appropriate Institutional Review Board (IRB) in accordance with local laws and regulations. The Investigator is responsible for maintaining documentation in the study file that indicates the IRB has been properly notified.

## 10.6 SAE FOLLOW-UP

All subjects experiencing an SAE, including the discontinued subjects, must be closely followed until sufficient information is obtained to indicate a return to normal status or until the event stabilizes at a level acceptable to the investigator (i.e., recovery, return to baseline status, no further improvement expected, or death).

For each SAE indicated as an unresolved event on the initial report, regardless of whether the subject completed the study or withdrew, the site should submit a follow-up report with updated information.

## 11 DIRECT ACCESS TO SOURCE DATA/DOCUMENTATION

Subjects will be identified on CRFs by a unique subject identification number and on source documents by name and date of birth. No personal identifier will be used in any publication or communication used to support this research study. The subject identification number will be used if it becomes necessary to identify data specific to a single subject.

The monitors, auditors, personnel authorized by the Sponsor, the local IRB, and the FDA are eligible to review medical and research records related to this study as a part of their responsibility to protect human subjects in clinical research and will be given direct access to source data and documentation (e.g., medical charts/records, printouts etc.) for source data verification, provided that subject confidentiality is maintained in accordance with local requirements. Access to electronic medical records may be governed by institution policy and each site will be required to ensure access while remaining compliant with institutional requirements.

## 12 DATA SAFETY MONITORING COMMITTEE (DSMC)

A Data Safety and Monitoring Committee (DSMC), independent of the study operations will be established to consider safety data generated during the study. The details of the DSMC responsibilities will be included in the DSMC charter. The DSMC charter will be developed and operated in adherence to the current FDA guidance on DSMC (Establishment and Operation of Clinical Trial Data Safety Monitoring Committees [March 2006]). The DSMC meetings will take place at least once and at other time-points as determined by the DSMC charter. In addition to the pre-specified time-points, the DSMC may also decide to schedule a meeting whenever they decide a review of emergent safety data is warranted. The charter will detail the roles and responsibilities of the DSMC members once they have been appointed. The study data will be provided to the Committee members in the form of a data report. Meetings to discuss the data will be held in person or by teleconference, based on the DSMC Chair's decision. The meetings will be in two stages: an "open stage" which will involve discussion on general aspects of the trial, and a "closed stage" between the DSMC members only. The remit of the DSMC will be primarily to assess the safety aspects of the trial.

## 13 QUALITY CONTROL AND QUALITY ASSURANCE

### 13.1 MONITORING REQUIREMENTS

In an effort to fulfill the obligations outlined in 21 CFR Part 312 and ICH guidelines which require the Sponsor to maintain current personal knowledge of the progress of a study, the Sponsor's designated monitor will visit the center(s) during the study as well as maintain frequent telephone and written communication. The Investigator will permit the Sponsor to monitor the study as frequently as is deemed necessary and provide access to medical records to ensure that data are being recorded adequately, that data are verifiable and that protocol adherence is satisfactory.

The Investigator will permit representatives of the Sponsor and/or designated CRO to inspect all CRFs and corresponding study subject original medical records (source documents) at regular intervals throughout the study. Subject original medical records and other relevant data must be available to support all data recorded in the CRF. In addition to the original medical records, these data may include but are not limited to, study, laboratory and diagnostic reports, wound images and tracings, etc.

Site inspections serve to verify strict adherence to the protocol and the accuracy of the data being entered on the CRFs, in accordance with federal regulations. A Monitoring Log will be maintained at each study site that the monitor will sign, date, and state the type of visit.

The Investigator should be aware that the study site and subject records may be inspected by the Sponsor and or representatives of the designated CRO, FDA, or other regional regulatory authority.

The final statistical analysis of data will be performed after all clinical monitoring has been completed, all data queries have been resolved, and all data have been verified (Quality Control checked) prior to formal database lock. The Sponsor will authorize the final database lock.

### 13.2 ACCEPTABILITY OF CASE REPORT FORMS

All CRFs will be completed as soon as possible after the subject's visit. Corrections to data on the CRFs will be made according to standard data correction procedures. The Investigator will review CRFs to indicate that, to his/her knowledge, they are complete and accurate. CRFs will be reviewed by the Sponsor's or designated CRO's monitor, who will make a decision as to their acceptability.

### 13.3 MODIFICATION OF PROTOCOL

The Investigator will not modify or alter this protocol without first obtaining the concurrence of the Sponsor. Approval by the Investigator's IRB must also be obtained prior to implementation of the change, with two exceptions:

1. When necessary to eliminate apparent immediate hazard to the subject; or
2. When the modification does not involve the subject's participation in the trial.

An amendment may also require modification of the ICF. The Investigator will provide an approval letter for the amendment and revised ICF, if applicable, to the Sponsor. An amendment must be in

---

writing and it must be dated by both the Sponsor and the Investigator. If necessary, the Sponsor will submit protocol amendments to FDA and other appropriate regulatory authorities and notify other Investigators using this protocol.

### **13.4 REPORTING PROTOCOL DEVIATIONS**

The Investigator is obligated to follow the protocol without departure from the requirements written in the protocol. If the Investigator deviates from the protocol requirements, the Sponsor will make the determination as to whether the subject will continue in the study. The Sponsor also has the right to discontinue the subject for protocol violations. The IRB may also have to be contacted if safety to the subject or if the scientific soundness of the study is involved. All protocol deviations must be documented in the CRFs.

